4.5.5 Vital Signs, Physical Findings, and Other Observations Related to Safety

4.5.5.1 Vital Signs

Vital sign parameter measurements will be summarized by study phase and cohort. Descriptive statistics will be presented for results and change from baseline at each visit where parameters were scheduled to be collected.

4.5.5.2 12-Lead Electrocardiogram

Twelve-Lead ECG interval parameters will be summarized by study phase and cohort. Descriptive statistics will be presented for observed values and changes from baseline

at each visit where parameters were scheduled to be collected. For select visits, the ECGs will be performed in triplicate and the mean of these triplicate measurements at each timepoint will be used for summarization.

Twelve-lead ECG will be classified by the investigator as “normal,” “abnormal, not clinically significant,” or “abnormal, clinically significant.” Three-by-three contingency tables will be presented to summarize the shift from the baseline category to the worst post-baseline value. Summary results will include the count and percentage of patients within each shift category and cohort.

Prolonged QTc intervals will be summarized as QTc measurements (msec) that are >450, >480, and >500 at each visit where ECG is routinely collected per the clinical study protocol. Change from baseline categories will also be summarized for measurements that represent a change >30 or >60 relative to the baseline value. Summary results will include the percentage of patients within each category and cohort.

Clinically significant abnormalities occurring at any point in the study post-baseline will be presented in patient-data listings.

4.5.5.3 Physical Examination

Results of the physical examination will be presented in patient data listings by patient, study visit, and body system. Any findings during symptom-directed exams will be reported as AEs.

4.5.5.4 Performance Status Assessments

Performance status will be assessed using either the ECOG or KPS. Karnofsky grades will be converted to the equivalent ECOG grade using the conversion table provided in Table 16 of the clinical study protocol. Performance status will be summarized by study phase and cohort. Descriptive statistics will be presented for observed values and changes from baseline at each visit where assessments were scheduled to be collected per the clinical study protocol. Results will be presented in patient data listings.

4.5.5.5 CMV Viral Loads

Patient’s CMV viral loads will be presented in patient data listings only.

4.5.5.6 Prior and Concomitant Medications

Medications will be coded using the World Health Organization Drug Dictionary Enhanced (WHODDE), version September 1, 2017. Medications entered on the eCRF will be mapped to Anatomical Therapeutic Chemical (ATC) drug class (level 4) and drug name.

Prior and concomitant medications will be summarized separately, and the categorization of each medication will be determined programmatically based on medication start and end dates. A prior medication is defined as any medication administered prior to the date of the first dose of study drug with an end date prior to date of first dose of study drug. A concomitant medication is defined as any medication

administered on or after the date of the first dose of study drug through 28 days after the last dose of study medication. Any medication whose start date/time cannot be determined due to partial or missing medication start and/or end dates, will be considered a concomitant medication.

For both prior and concomitant medications summaries, the number and percentage of patients receiving any medication will be summarized by cohort, as will the number and percentage receiving any medication by ATC drug class and generic drug name. Prior medications will also be summarized over all patients combined. Patients reporting use of more than one medication at each level of summarization (any medication received, ATC class, and generic drug name) will be counted only once. ATC class terms will be displayed by descending order of incidence, as will generic drug names within each ATC class. The study phase during which each medication was received (e.g., prior, concomitant, or both) will be presented on the listing of prior and concomitant medications.

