3.14. Prohibited Cancer Treatments

The following medications/therapies intended to treat the patients' underlying cancer are prohibited during the study

- Other investigational agents
- Other cancer therapies other than those which the patient has received for at least 6 months and which the Investigator, Medical Monitor, and Sponsor representative agree are unlikely to interfere with the study objectives (e.g., hormonal therapy for prostate cancer)

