Informed consent – Informed consent may be performed at any time prior to the start of screening procedures.

EBER/histology Sample – Histology sample, indicative of current disease, to be sent to central pathology lab at the time of screening. Central pathology review/results not required for enrollment. Pathology review will include detection of EBV gene products.

Medical history – Record all cancer-related history over the patient's lifetime and collect non-cancer related history for the 2 years prior to study entry. For transplant recipients (except auto-SCT), collect the following historical information on donors: HIV1, HIV2, hepatitis B surface Ag, hepatitis B surface Ab, hepatitis B core Ab, hepatitis C Ab, HSV-1 Ab, HSV-2 Ab, CMV Ab IgG, CMV Ab IgM, EBV IgG-VCA (viral capsid antigen).

Vital signs – Performed just prior to first dose of valganciclovir and VRx-3996, and in concert with (but prior to) PK draws on Cycle 1 Day 1. On other indicated visit days, perform vital signs once (prior to study drugs dosing if administered in clinic). Vital signs include weight (in pounds), heart rate, respiratory rate, blood pressure, temperature, and oxygen saturation by pulse oximeter. Note that weight only needs to be recorded once daily.

Performance status – Either ECOG or KPS (See [Table 16](#) in the Appendix for conversion table).

Concomitant medications – Recorded from 28 days prior to Cycle 1 Day 1 to 28 days after last dose of study drugs, except for concomitant medications related to cancer treatment, for which lifetime history prior to entering the study will be recorded.

Urinalysis – [Urine] Color, appearance, glucose, bilirubin, ketone, specific gravity, blood, pH, protein, urobilinogen, nitrite, leukocyte esterase, RBC, WBC, epithelial cells.

Hematology - [Blood] Complete blood count with differential to include WBC, RBC, HGB, HCT, platelets, MCV, MCH and differential.

Chemistry - [Blood] Sodium, potassium, chloride, bicarbonate, blood urea nitrogen, creatinine, glucose, calcium, phosphate, magnesium, AST, ALT, total bilirubin, alkaline phosphatase, total protein, albumin, uric acid, and LDH.

Coagulation – [Blood] PT, PTT, and INR.

Serum pregnancy test – Only required for females of child-bearing potential.

Urine pregnancy test – Only required for females of child-bearing potential at the beginning of every cycle.

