4.5.2 Adverse Events

Treatment-emergent adverse events (TEAEs) are defined as those adverse events (AEs) with onset after the first dose of study drug or pre-existing events that worsened by at least one grade after the first dose during the study. Treatment-emergent AEs will be summarized by study phase and cohort. Events reported with a partial onset date (e.g., month and year are reported but the day is missing) will be considered to be treatment-emergent if it cannot be confirmed that the event onset was prior to the first dose of study drug based on the available date entries.

Verbatim terms on case report forms will be mapped to preferred terms and system organ classes using the Medical Dictionary for Regulatory Activities (MedDRA, version 25.0). As an additional safety analysis, certain hematological AEs will be programmatically re-mapped to preferred terms and system organ classes consistent with CTCAE v5.0 categories. Select AE summaries will be repeated using this alternative mapping.

Summaries that are displayed by system organ class and preferred terms will be ordered by descending incidence of system organ class and preferred term within each system organ class. Summaries displayed by preferred term only will be ordered by descending incidence of preferred term. Summaries of the following types will be presented:

- Overall summary of number of unique TEAEs and patient incidence of TEAEs meeting various criteria.
- Overall summary of number of unique SAEs and patient incidence of SAEs meeting various criteria
- Patient incidence of TEAEs by MedDRA system organ class and preferred term
- Patient incidence of TEAEs by CTCAE toxicity grade, MedDRA system organ class, and preferred term.
- Patient incidence of dose-limiting toxicity AEs by MedDRA system organ class and preferred term.
- Patient incidence of TEAEs leading to dose interruption, reduction or discontinuation of valganciclovir by MedDRA system organ class and preferred term.
- Patient incidence of TEAEs leading to reduction or interruption of nanatinostat and valganciclovir by system organ class and preferred term
- Patient incidence of TEAEs leading to discontinuation of nanatinostat and valganciclovir by system organ class and preferred term

- Patient incidence of SAEs by MedDRA system organ class and preferred term.
- Patient incidence of SAEs by CTCAE toxicity grade, MedDRA system organ class, and preferred term.

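### The SAP's incomplete-date rule for medications tests the start date, while prior status depends on the end date, so a medication that clearly stopped before first dose can be classed as concomitant

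*SAP*

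**What the plan says.** SAP 4.5.5.6 tabulates prior and concomitant medications separately and leaves the split to a program: "the categorization of each medication will be determined programmatically based on medication start and end dates". A prior medication is one given before first dose "with an end date prior to date of first dose of study drug". A concomitant medication is one "administered on or after the date of the first dose of study drug through 28 days after the last dose of study medication". Incomplete dates are then handled in one sentence, which covers any medication whose start date or time "cannot be determined due to partial or missing medication start and/or end dates, will be considered a concomitant medication".

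Two other places bear on this. For adverse events with a partial onset date, SAP 4.5.2 makes the event treatment-emergent only "if it cannot be confirmed that the event onset was prior to the first dose of study drug based on the available date entries". In the Protocol, the Section 7 note on concomitant medications limits recording to a window around treatment, "except for concomitant medications related to cancer treatment, for which lifetime history prior to entering the study will be recorded".

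**The concern.** The definition of prior rests on when a medication stopped. The fallback rests on whether its start is known. These are different dates, and for an old, finished treatment the start date does not decide the class. A record with an unknown start day and a complete stop date well before first dose satisfies the definition of prior, yet the fallback sends it to concomitant. A programmer cannot obey both sentences.

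The case is realistic here. Patients must have relapsed or refractory disease and have failed available standard therapy (Protocol 4.1). Their cancer treatment is recorded over a lifetime under the concomitant medications assessment, and incomplete dates are to be expected in old records. SAP 4.5.5.6 gives no separate handling for such records.

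If they pass through these tables, an earlier antibody or chemotherapy regimen could be shown as given during the study and be absent from the prior table. Protocol 3.14 prohibits cancer treatment on study, with an exception: "Other cancer therapies other than those which the patient has received for at least 6 months" and which are agreed to be unlikely to interfere with the study objectives. The concomitant table could then suggest breaches that did not occur, or make real ones harder to pick out.

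**Working it through.** The plan states no figure on this point, so there is none to reproduce. The check is one of logic: apply the rules to records with different date patterns. The records are illustrative, with an assumed first dose of 15 June 2020. Two tests are compared.

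- **SAP as worded:** an incomplete start date triggers the fallback, giving concomitant. If both dates are complete, the end date decides.
- **Known-parts test**, on the pattern of the adverse-event rule: prior if the latest date compatible with the known parts of the stop date falls before first dose; otherwise concomitant.

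| Record | Start | Stop | SAP as worded | Known-parts test |
|---|---|---|---|---|
| 1 | 2 Mar 2015 | 10 Aug 2015 | Prior | Prior |
| 2 | 2015 | 10 Aug 2015 | Concomitant, but also meets the prior definition | Prior |
| 3 | Mar 2015 | Aug 2015 | Concomitant | Prior |
| 4 | 2 Mar 2015 | Aug 2015 | Fallback not triggered; no rule for the partial stop | Prior |
| 5 | 2 Mar 2015 | 2015 | Fallback not triggered; no rule for the partial stop | Prior |
| 6 | 2015 | 2015 | Concomitant | Prior |
| 7 | missing | 10 Aug 2015 | Concomitant, but also meets the prior definition | Prior |
| 8 | May 2020 | Jun 2020 | Concomitant | Concomitant |
| 9 | 2 Mar 2015 | missing | Fallback not triggered; no rule for the missing stop | Concomitant |

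Records 2 to 7 are the six that have an incomplete date and ended in 2015.

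- Four of the six (2, 3, 6, 7) have an incomplete start and become concomitant under the SAP as worded.
- In two of those four (2 and 7) the stop date is complete and before first dose, so the SAP contradicts itself.
- The other two (4 and 5) have a complete start and a partial stop. The fallback does not reach them, and nothing says whether a known year or month counts as an end date.

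Under the known-parts test all six are prior. Records 8 and 9, whose timing is truly uncertain, stay concomitant, so the cautious default is kept where it is needed.

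Setting the two SAP rules side by side leads to the same place. The adverse-event rule (4.5.2) first asks what the available date parts can confirm, and applies its default only if they cannot. The medication rule (4.5.5.6) goes straight to the default.

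**The case against.** The best defence is that the sentence should not be read so literally. A missing end date cannot make a start date undeterminable, so mentioning end dates suggests that the author meant timing relative to first dose. On that reading a 2015 regimen is plainly placed before first dose, the prior definition applies, and nothing goes wrong. This is a sensible intention, and the SAP nowhere says that known date parts are to be ignored. But the sentence names the start date, and a program will be written from it. A middle reading, that the start cannot be placed relative to first dose, rescues the 2015 records but leaves record 9 uncovered: its start is known and its stop is not. The sentence therefore needs rewriting unless overall timing is substituted for the start date it names, and that substitution is the fix.

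Defaulting uncertain timing to concomitant is also conservative. That stands for uncertain timing, but not for a stop date known to precede first dose.

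Third, lymphoma treatment may not reach this table. The Protocol's medical history note also asks for lifetime cancer history, and SAP 4.4 summarises lymphoma history separately. The documents do not say which eCRF page feeds the medication tables, so the consequence for old regimens is conditional.

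Finally, listings show the collected data, and eligibility requires at least 14 days since anti-lymphoma therapy (7 with approval). A careful reader could often recognise an old regimen from its dates. That limits the harm but does not correct the table.

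**Conclusion.** The point holds as a defect in a stated rule. Read literally, SAP 4.5.5.6 gives the wrong class to a medication with an incomplete start and a stop clearly before first dose, and gives no class to one with a complete start and a partial stop. The effect falls on the descriptive prior and concomitant tables and the related listing. It reaches old lymphoma regimens only if their start dates are incomplete and they are processed through these tables.

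The documents do not support several stronger conclusions that a reader might draw:

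- **That any partial start or end date makes a medication concomitant.** The trigger is an undeterminable start date; a partial stop alone is a gap. The text makes four of the six illustrative records concomitant, not six.
- **That response or progression results are affected.** SAP 4.6.2 and Table 4 do not use this flag. ORR rests on the investigator's response assessment, and the PFS and DoR censoring rule concerns new anti-cancer therapy started before progression or death.
- **That the prior-therapy subgroups in SAP 4.6.5.8 are miscounted.** That section does not say where its count comes from.
- **That a share of patients can be stated.** Assuming 2 to 3 earlier regimens with 20% to 50% of start dates partial gives 1 − 0.8² = 36% to 1 − 0.5³ = 87.5%. Neither input is in the documents, and the formula assumes that partial dates occur independently within a patient, that every regimen enters this table, and that the literal reading applies. No percentage should be quoted.

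**What to change.** Replace the fallback sentence in SAP 4.5.5.6 with wording that matches the adverse-event rule, for example: *A medication with partial or missing dates is considered concomitant unless the available date entries confirm that it ended before the first dose of study drug, in which case it is considered prior.*

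This keys the rule to the same date as the definition of prior, covers the partial-stop gap, and leaves the cautious default for a missing stop or one known only to the month of first dose. It would also help to state whether lifetime cancer treatment is summarised in these tables or elsewhere. The cost is one SAP sentence and a small programming change; no new data are needed.

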4.6 Efficacy Evaluation

4.6.1 Datasets Analyzed

All efficacy summaries will be based on the EES. A data listing of patients excluded from the EES, to include the reason for exclusion, will be presented.

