12. STATISTICAL CONSIDERATIONS

12.1. Analysis Datasets

This study will identify the following datasets:

- Intent to treat dataset: All patients who have enrolled in the study
- Safety dataset: All patients who receive at least 1 dose of VRx-3996.
- Efficacy dataset: All patients with measurable disease at Screening who have met all inclusion criteria and have received at least 1 post-baseline tumor assessment for efficacy.

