3.4.2 Efficacy Variables

3.4.2.1 Primary Efficacy Variable

The primary efficacy endpoint is the ORR, defined as the proportion of patients with a best overall response of complete response (CR) or partial response (PR) according to the Lugano criteria ([Cheson 2014](#)).

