4.1.1 Reporting Conventions

Tables and figures will be summarized by cohort and study phase. Tables will also include a column for all patients who receive the capsule formulation. In general, all data collected, and any derived data will be presented in patient data listings, for all enrolled patients. Listings will be ordered by site, study phase, patient number, cohort,

and assessment or event date. The cohort presented in listings will be based on the planned assignment, unless otherwise noted.

Summaries will be based on patient data from both the dose escalation and dose expansion phases up until the time when the final dose escalation patient has completed at least 12 months of follow-up from their first disease response assessment after two cycles of therapy, or until all patients have discontinued the study, died, withdrawn consent, discontinued, or are lost to follow-up, whichever occurs first.

In general, continuous variables will be summarized to indicate the study population sample size (N), number of patients with available data (n), mean, SD, median, minimum, and maximum values. Categorical variables will be summarized by the population size (N), number of patients with available data (n), number of patients in each category, and the percentage of patients in each category. Unless otherwise noted, the denominator to determine the percentage of patients in each category will be based on the number of patients with available data. Select ordinal data may be summarized using both descriptive statistics and counts and percentages of patients in each category, as appropriate.

Non-zero percentages will be rounded to one decimal place. Rounding conventions for presentation of summary statistics will be based on the precision of the variable of summarization, as it is collected in its rawest form (i.e., on the electronic case report form [eCRF] or as provided within an external file) and are outlined as follows:

- The mean and median will be rounded to one more decimal place than the precision of the variable of summarization.
- Measures of variability (e.g., SD, SE) will be rounded to two more decimal places than the precision of the variable of summarization.
- Minimum and maximum values will be presented using the same precision as the variable of summarization.

Other statistics (e.g., CIs) will be presented using the same general rules outlined above or assessed for the most appropriate presentation based on the underlying data.

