4.2 Analysis Sets

The analysis sets are defined as follows:

- Intent-to-Treat (ITT) Set: The ITT includes all enrolled patients.
- Safety Analysis Set: includes all enrolled patients who receive at least one dose of nanatinostat.
- Efficacy Evaluable Set: includes all patients with measurable/evaluable disease at screening who have met all eligibility criteria and have at least one evaluable post-baseline efficacy tumor assessment.
- Pharmacokinetic Analysis Set: includes all patients in the ITT who have received at least one post-dose PK sample obtained and analyzed (i.e. valid result being

available). The PK Analysis Set is used for tabulation of nanatinostat and ganciclovir concentrations from PK plasma samples.

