4.6.5.2 Handling of Dropouts or Missing Data

Best overall response is based on those patients with available data (baseline and post-baseline response assessment). Non-evaluable patients are considered non-responders and will be included in the denominator. Progression-free survival and DoR will be right-censored for patients who met one of the following conditions: 1) non-protocol systemic anti-cancer treatment started before documentation of disease progression or death, 2) death or disease progression after more than one missed disease assessment visit, or 3) alive and does not have documentation of disease progression before a data analysis cutoff date. These conventions are based on the FDA Guidance for Industry, *Clinical Trial Endpoints for the Approval of Cancer Drugs and Biologics* (2018). The analysis of PFS and DoR will be right-censored according to the conventions described in [Table 4](#).

Table 4 Conventions for Censoring for PFS and DoR

Situation	Date of Progression or Censoring	Outcome
New anti-cancer therapy started before documentation of PD or death	Date of last disease assessment prior to start of new anti-cancer therapy	Censored
Death or PD immediately after more than one consecutively missed disease assessment visit	Date of last disease assessment visit without documentation of PD that is before the first missed visit	Censored
Alive and without PD documentation	Date of last disease assessment	Censored
Death or PD between planned disease assessments	Date of death or first disease assessment showing PD, whichever occurs first	Progressed
Death before first disease assessment	Date of death	Progressed

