4.6.5.6 Use of an “Efficacy Subset” of Patients

The efficacy analysis will be performed on the Efficacy Evaluable Set, which is a subset of the ITT Set.

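### The SAP gives the primary response rate (and the disease control rate) conflicting denominators: patients without an evaluable post-baseline assessment are both excluded and counted as non-responders

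*SAP*

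**What the plan says.** SAP 3.4.2.1 describes ORR as "defined as the proportion of patients with a best overall response of complete response (CR) or partial response (PR" by the Lugano criteria, without saying which patients form the denominator. Other sections fill the gap in different ways.

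- **EES.** SAP 4.6.1: "All efficacy summaries will be based on the EES". SAP 4.6.5.6 repeats it: "The efficacy analysis will be performed on the Efficacy Evaluable Set, which is a subset of the ITT Set". Under SAP 4.2, members must meet all eligibility criteria and "have at least one evaluable post-baseline efficacy tumor assessment".
- **Available data.** SAP 4.1.1 sets a general default, unless otherwise noted: "the denominator to determine the percentage of patients in each category will be based on the number of patients with available data". SAP 4.6.5.2 opens in the same way: "Best overall response is based on those patients with available data (baseline and post-baseline response assessment".
- **Non-evaluable patients kept.** The next sentence of SAP 4.6.5.2 reads: "Non-evaluable patients are considered non-responders and will be included in the denominator".

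SAP 4.6.3 applies the ORR methods to DCR. Protocol 12.1 defines an efficacy dataset whose members must "have received at least 1 post-baseline tumor assessment for efficacy"; the SAP adds the requirement that the assessment be evaluable. SAP 4.9, which lists changes from the protocol, mentions none of this.

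**The concern.** The primary efficacy rate cannot be computed without choosing between the SAP's own rules, and the set named in 4.6.1 depends partly on outcome. The first scheduled disease assessment follows Cycle 2, about 56 days after the start (two 28-day cycles). Protocol Table 15 also lists an assessment at End of Treatment, but when treatment stops between visits, protocol 6.3.1 promises only an attempt to bring the patient back. In a relapsed or refractory population, some patients may die or deteriorate with no assessment at all. The plan anticipates them: protocol 3.18 allows their replacement in Phase 2, and SAP Table 4 has a rule for death before the first assessment.

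Such patients are likely non-responders, so leaving them out probably raises ORR and DCR. SAP 4.6.5.5 plans no hypothesis test, so the estimate and its interval are the efficacy result. An open choice of denominator in an open-label study with investigator-assessed response is the kind of post hoc decision that SAP Section 1 says the plan exists to prevent.

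**Working it through.** **1. The plan's own figures.** SAP 4.8 gives a two-stage design with 10 then 29 patients, response rates of 5% and 20%, early stopping probability 59.9%, type I error 0.0468 and power 80%. Stopping after 0 of 10 responses has probability 0.95^10 = 0.5987. The final cut-off is not stated; rejecting at 4 or more responses in 29 gives type I error 0.0468 and power 0.8011. The design figures reproduce and are not in dispute. The futility rule is worded in terms of treated patients.

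**2. The rules applied to one patient type.** Take a treated patient with no evaluable post-baseline assessment.

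- SAP 4.2 with 4.6.1 and 4.6.5.6: not in the EES, so out of the denominator.
- SAP 4.6.5.2, first sentence: out if never assessed; arguably in if assessed with a not-evaluable result.
- SAP 4.6.5.2, second sentence: in, as a non-responder.

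Inside the EES the last rule has almost nobody to act on, because a patient with only not-evaluable results never enters. To have effect it must reach beyond the EES, and the SAP does not say whether to all patients or only to those assessed.

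**3. Three rates from the same data.** Assumed counts: 30 treated (the Phase 2 size), 6 responders (chosen to match the 20% design rate), 3 never assessed, 2 assessed but not evaluable. The interval is Clopper-Pearson, as in SAP 4.6.2: the lower limit is the 0.025 quantile of Beta(x, n−x+1), and the upper limit is the 0.975 quantile of Beta(x+1, n−x).

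- All treated: 6/30 = 20.0% (95% CI 7.7–38.6%)
- Assessed, not-evaluable results kept: 6/(30−3) = 6/27 = 22.2% (8.6–42.3%)
- EES as defined: 6/(30−3−2) = 6/25 = 24.0% (9.4–45.1%)

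**4. General size.** If a share d of treated patients is dropped and all are non-responders, the rate is multiplied by 1/(1−d): 1.11, 1.25 or 1.43 for d = 10%, 20% or 30%. The DCR columns assume 12 patients with disease control, none of them dropped.

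| d (assumed) | ORR | 95% CI | DCR | 95% CI |
|---|---|---|---|---|
| 0% | 6/30 = 20.0% | 7.7–38.6% | 12/30 = 40.0% | 22.7–59.4% |
| 10% | 6/27 = 22.2% | 8.6–42.3% | 12/27 = 44.4% | 25.5–64.7% |
| 20% | 6/24 = 25.0% | 9.8–46.7% | 12/24 = 50.0% | 29.1–70.9% |
| 30% | 6/21 = 28.6% | 11.3–52.2% | 12/21 = 57.1% | 34.0–78.2% |

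Tablet cohort of 10: 2/10 = 20.0% (2.5–55.6%) becomes 2/8 = 25.0% (3.2–65.1%) if two are dropped.

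**5. Opposite direction.** The EES also removes ineligible patients. If 3 of 30 are removed for eligibility and 1 of them had responded, the rate falls to 5/27 = 18.5% (6.3–38.1%).

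**6. Time-to-event endpoints.** Table 4 (PFS and DoR only) counts a death before the first assessment as an event, and SAP 4.6.3 plans survival curves for everyone who received study treatment. Read literally, neither fits an EES-only analysis.

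**The case against.** Two sections name the EES, and the 4.1.1 default yields wherever something else is noted, so it is not a true rival. The two sentences of 4.6.5.2 can be read together: the first sets the population (assessed after baseline), and the second counts a not-evaluable result within it as non-response. That matches protocol 12.1, and it would shrink the dispute to one word in SAP 4.2, or 22.2% against 24.0% in the example. The analysis is descriptive, the intervals overlap heavily, and every count is assumed. The patient listings (4.1.1, 4.6.1, 4.6.2, 4.6.3) and analysis-set counts (4.3.1) would let anyone holding them recalculate any version exactly. Changing the main population late in an open-label study also has a credibility cost.

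The points on the 4.1.1 default and the listings stand, but neither removes the conflict. The joint reading of 4.6.5.2 still contradicts the evaluable requirement in 4.2. The listings supply the information without prespecifying the rate or its interval. Nor is an all-treated set merely a reviewer's preference. Section 4.6.5.2 is about dropouts and missing data, Table 4 covers deaths before assessment, the curves in 4.6.3 cover everyone treated, and the futility rule counts treated patients.

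**Conclusion.** The concern holds. The SAP places a patient without an evaluable post-baseline assessment both inside and outside the ORR denominator; DCR follows by cross-reference, and nothing in the SAP settles it. In the worked Phase 2 example the choice moves ORR by 4.0 percentage points (20.0% to 24.0%). If 10% to 30% of treated patients are dropped as non-responders, the rate is inflated by a factor of 1.11 to 1.43.

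These sizes rest on assumed counts. The probable direction is upward, because early losses are likely non-responders, though eligibility exclusions could reverse it. No effect on type I error or overall survival is claimed. Because the primary efficacy estimate is undefined as written, this should be corrected before the analysis is run.

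**What to change.** - In SAP 4.6.1, 4.6.5.2 and 4.6.5.6, make all treated patients (the Safety Analysis Set) the main set for ORR and DCR. Count those without an evaluable post-baseline assessment as non-responders, and as not controlled for DCR.
- Define non-evaluable as covering both never assessed and assessed with a not-evaluable result.
- Keep replaced patients in the denominator, and state that this overrides the 4.1.1 default.
- State in 4.6.3 that PFS and OS use all treated patients, with deaths before the first assessment as events.
- Keep the EES of 4.2 as a labelled sensitivity analysis.
- Record in 4.9 the change from the protocol's efficacy dataset.

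The cost is SAP wording and a repeated set of efficacy tables, including the subtype and subgroup displays; no new data or patients are needed. The headline ORR would probably be lower (20.0% instead of 25.0% when 20% are dropped). The main set would also include any patient later found ineligible, for example if central retesting did not confirm EBV; the EES analysis shows their effect. If the change comes late, stating it openly in 4.9 and reporting both sets limits the credibility cost.
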